C3c. PDD Behavioral Analysis: Amplitude Modulated Regression (AMR): Within-subject AMR will be carried out using AFNI package 3dDeconvolve. AMR is performed by scaling the expected hemodynamic response on a trial-by-trial basis according to the magnitude of each specific characteristic on that trial. In addition to the inclusion of trial-by-trial modulated predictors, a constant amplitude predictor is included for each to identify regions that respond to the stimulus but did not vary according to its value. The general linear model (GLM) will include amplitude-modulated predictors for the presentation of the three reward characteristics to identify blood oxygen level dependent (BOLD) signals that scale parametrically with probability, delay or magnitude. Group differences will be tested on the set of *a priori* ROIs (**Table 3**) identified in **PS1** and literature. This analysis will calculate decision profiles for each subject with values that represent sensitivity to delay, risk and magnitude.

Hypothesis 1a.1: Individuals co-addicted to alcohol and nicotine will exhibit a pattern of cortical activation to delay, magnitude and probability characterized by both increased sensitivity to reward in striatum and aversion to risk and delay in dorsal cognitive control regions.

reward in salience network regions and modestly greater sensitivity to delay and probability in executive regions, (2) AUD subjects will exhibit greater sensitivity in all regions compared to CS and NUD. (3) The co-addicted, NAUD, group will show greater sensitivity to delay and probability in dorsal cognitive control regions (**Error! Reference source not found.; Table 3**) than the AUD group and a similar pattern, but smaller effect size between the NUD and CS groups. The combination of these effects is predicted to increase discounting of delayed and probabilistic rewards. For this and all our hypotheses concerning the co-addicted groups, our initial prediction is that the groups will show a synergistic effect of nicotine and alcohol. It is possible, however, that there is a simply additive or even an antagonistic effect of the two drugs. Our analysis will differentiate among these possibilities.

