C6d. Interpretation: Alcohol and Smoking Groups: We expect that this method will identify a set of brain regions, their function and their connectivity that will differentiate NAUD and AUD groups from each other, from NUD and from CS. We expect that we will confirm damage to white matter microstructure in long tracts connecting, in particular the PPC (AG, IPL) with frontal regions (DLPFC, VMPFC, ACC). We expect functional abnormalities in the salience circuit. We predict that these neural abnormalities will be more pronounced in alcohol users than nicotine users but that co-addicted individuals will exhibit the highest level of abnormality. **Outcome:** We expect that decreased cortical density, sensitivity to cues and reward characteristics, increased FA, poor functional connectivity and co-addiction to smoking will predict poor outcome in the AUD and NAUD groups. We specifically expect that functional and anatomic deficits in salience and, especially, cognitive control regions will be important predictors of outcome.

C7. Specific Methods: Human MRI Imaging Acquisition: We will use the Human Connectome Project (HCP) Lifespan Protocol using a 3T Siemens Magnetom Prisma scanner and a 32-channel phased array head coil. **fMRI (T₂^{*}-weighted):** Three (2 PDD and 1 DSNBACK) T₂^{*}- weighted echo-planar imaging (EPI) functional runs will be acquired (60 slices, 2 mm thick, TR/TE/α=2000 ms/38 ms/55°, matrix=128 × 128, FOV=220 mm², [name]

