PAT mode/Accel factor = GRAPPA/2, 310 volumes per run) with an in-plane pixel size of 2.0 mm² while subjects perform the PDD or the DSNBACK. Each run will be 10.3 minutes long. **rsfMRI**: Identical to fMRI settings with 200 volumes. **High-resolution anatomical (T_1 -weighted [T_{1w}])**: One magnetically prepared rapid acquisition gradient echo (MPRAGE) (208 0.8 mm isovoxels, TR/TE/TI/α = 2400 ms/2.24 ms/1060 ms/8°, FOV=256x240 mm, 2x Parallel Imaging, duration 6.38 min), will be acquired for co-registration with functional images and statistical overlay. **High-resolution anatomical (T_2 -weighted [T_{2w}])**: 208 slices, 0.8 mm isovoxels, TR/TE: 3200 ms/564 ms; variable flip angle; FOV 256x263 mm, 2x Parallel imaging; Futsyion 5.57 min. **HARDI**: Two HARDI scans will be acquired (66 axial slices, 2.2 mm thick, TR/TE/α = 4300 ms/96 ms/90°, FOV= 25.6 cm², PAT mode /Accel factor = GRAPPA/2) consisting of six non-diffusion weighted (B_0) images followed by 32 non-collinear directions at $B_0 = 1000$ s mm⁻² and at $B_0 = 2000$ s mm⁻². Each HARDI scan lasts 4.73 min.

C7a. fMRI Standard Preprocessing: Task-related and resting-state fMRI data will be preprocessed identically. We include only scans with minimal movement (< 3 mm) and free of artifacts (Murphy et al., 2013). Functional images will be realigned for motion corrections, unwarped then co-registered to structural images for each subject and then transformed to Talairach coordinates and then resampled into atlas space with 3 mm isovoxels. Motion correction is applied with the standard 6 parameters and then frame-by frame spatial deviations are assessed with the temporal derivative of the time course. The anatomical volume is then

segmented into gray matter, white matter, and cerebrospinal fluid. Next, we apply a temporal bandpass filter (0.009 Hz < v < 0.08Hz), spatial smoothing (6 mm full width at half maximum (FWHM) Gaussian kernel), regression with the 6 rigid body motion parameters, regression of the whole brain signal and regression of the signal for ventricles and white matter. Opposite phase-encode polarity spin echo images will be used to estimate the B_0 distortion field, which will be applied to each gradient echo frame after accounting for estimated head motion. Gradient nonlinearity distortions will be corrected using scanner-specific field maps. Both corrections are vital for proper registration to structural images. Images will

[figure not shown]

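### C7a as written applies whole-brain signal regression and a resting-state band-pass to the task fMRI, while a second list in the same section omits both; the plan must say which governs the PDD and DSNBACK runs

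*Combined protocol and SAP*

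**What the plan says.** C7a (fMRI Standard Preprocessing) opens with "Task-related and resting-state fMRI data will be preprocessed identically". The list that follows includes "we apply a temporal bandpass filter (0.009 Hz < v < 0.08Hz" and "regression of the whole brain signal and regression of the signal for ventricles and white matter", together with 6 mm smoothing and transformation to Talairach space. Nothing exempts the PDD or DSNBACK runs.

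Later in C7a, after the Figure 3 caption, comes a second list built on AFNI programs: despiking, slice-timing and motion correction, alignment to the warped anatomical image, a 4 mm blur, and scaling of each voxel to a mean of 100. It mentions no temporal filter and no whole-brain regression. The anatomical images it aligns to are warped to MNI-152. The list is not labelled as belonging to task or rest.

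For the PDD, C3c says "The general linear model (GLM) will include amplitude-modulated predictors for the presentation of the three reward characteristics", fitted in 3dDeconvolve, with group differences then tested in the Table 3 ROIs. C3d describes the DSNBACK contrasts. Neither section says that the task regressors are filtered to match the data. C6 reuses the regional task coefficients as features of the SVM classifier.

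**The concern.** A narrow band-pass and whole-brain regression are connectivity steps. Applied to task data, they act on the signal that the task model is meant to estimate.

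Whole-brain regression is the more serious of the two. The whole-brain average includes the task response. Removing it takes away part of each subject's response, and how much depends on how widely that subject's brain responds. If groups differ in that extent, the step itself produces a group difference. C3c predicts effects of this broad kind: AUD subjects are expected to be more sensitive than CS and NUD across all the regions considered.

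The band-pass removes any part of the PDD modulated response above 0.08 Hz or below 0.009 Hz. If the data are filtered and the regressors are not, the coefficients shrink.

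The SA1a results rest on these coefficients, and the SA2 classifier inherits them.

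**Working it through.** **Inputs from the plan (C7 and C7a).** "TR/TE/α=2000 ms/38 ms/55" gives TR = 2 s; task runs have "310 volumes per run"; the band is 0.009-0.08 Hz. Trial spacing, block length, extent of activation and shared noise are not given, so they are assumed below and shown as ranges.

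**Run length.** 310 x 2 s = 620 s = 10.33 min, which agrees with "Each run will be 10.3 minutes long".

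**What the band keeps.** Fourier frequencies are k/620 Hz. Those inside the band run from k = 6 (0.0097 Hz) to k = 49 (0.0790 Hz): 44 frequencies, or 88 of 310 temporal degrees of freedom (28%).

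**PDD modulator variance outside the band.** Assumptions: a double-gamma haemodynamic response, a random four-level modulator, and trial spacings of 6-8, 8-12, 10-16 and 14-18 s. By simulation:
- below 0.009 Hz: about 9-10%
- above 0.08 Hz: about 12%
- total: about 21-22%

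Other assumptions (spacing from 4-8 s to 14-20 s, events of 2-6 s, normally distributed modulator) give 16-21%. With filtered data and unfiltered regressors, the coefficient shrinks by about the share lost.

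**DSNBACK.** For on/off blocks of length L the fundamental frequency is 1/(2L). It falls below 0.009 Hz when L exceeds 1/(2 x 0.009) = 55.6 s. In simple alternation, 96-99% of the variance is kept for 10-50 s blocks, but only about 20% for 60-80 s blocks.

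**Whole-brain regression.** Take V = 500 voxels with unit-variance independent noise, a unit-variance task regressor, shared noise of SD s, and a fraction p of voxels responding with coefficient B. The mean coefficient is m = pB. Write q = s² + 1/V. After the whole-brain mean is regressed out, a voxel with true coefficient b has expected coefficient

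(b - m) x q / (m² + q).

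Example: p = 0.1, s = 0.2, so q = 0.04 + 0.002 = 0.042.
- B = 1.0: m = 0.10; 0.90 x 0.042/0.052 = 0.727
- B = 1.5: m = 0.15; 1.35 x 0.042/0.0645 = 0.879
- The true group difference of 0.50 becomes 0.152 (simulation: 0.151).

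Group difference in the responding ROI when the truth is 0.50 (B = 1.0 against 1.5):

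| s | p | formula | simulation |
|---|---|---|---|
| 0.2 | 0.1 | 0.15 | 0.15 |
| 0.2 | 0.3 | -0.04 | -0.05 |
| 0.5 | 0.1 | 0.37 | 0.37 |
| 0.5 | 0.3 | 0.07 | 0.06 |
| 1.0 | 0.1 | 0.43 | 0.42 |
| 1.0 | 0.3 | 0.23 | 0.23 |

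Without the regression, the simulated differences were 0.50 to 0.52.

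Group difference when the true ROI coefficient is 1.0 in both groups but the extent is 30% against 10%: -0.50 (s = 0.2), -0.35 (s = 0.5) and -0.24 (s = 1.0) by simulation, and -0.50, -0.35 and -0.25 by formula. Non-responding voxels acquire coefficients of -0.08 to -0.37.

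**The case against.** **The second list may be the task pipeline.** This is a fair reading. Scaling to a mean of 100 is usual before a 3dDeconvolve model, and the conflicts in smoothing and target space suggest two merged pipelines. C4 also describes nuisance regression of its own for resting state. A reader might infer that the task data will certainly be filtered and globally regressed; the documents do not settle that. But the second list carries no label and does not withdraw the opening sentence, so the literal instruction stands and C7a needs an edit on either reading.

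**The band-pass does not by itself bias group contrasts.** This stands. If groups share trial timing, shrinkage is by a roughly common factor, and a group t-test is unaffected by a common scale. Much of the loss below 0.009 Hz would occur anyway: a 1/128 Hz high-pass removes 7-8% of modulator variance and a fifth-order polynomial 4-5%. Noise outside the band is removed too. Against a polynomial-drift model, within-subject signal-to-noise fell by only 9-12% (white or AR(1) noise, correlation 0-0.5), and the group-level loss is smaller once between-subject variance is added.

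**Keeping 88 of 310 degrees of freedom looks alarming.** A reader might infer that the group tests lose most of their information. They do not: C3c tests subject-level ROI values, and the degrees of freedom there come from the number of subjects.

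**The filter hardly touches a blocked task.** This stands for DSNBACK with blocks up to about 50 s. Block length is not stated.

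**The whole-brain figures rest on assumptions.** They do. How much is removed from a voxel depends on its loading on the global signal, so it would be wrong to say that each subject's average response is simply subtracted from every ROI. The direction of the threat does not depend on the particular values chosen.

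**Conclusion.** The point holds in this form: C7a, read literally, applies whole-brain regression and a 0.009-0.08 Hz band-pass to the task runs, and a second list in the same section leaves it unclear whether that is intended.

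If the literal rule is followed, whole-brain regression is the main threat to both tasks. Under the assumed extents and shared noise it ranges from mild attenuation of a true group difference to its complete loss, and it can create a difference with the opposite sign where none exists. The documents do not give the inputs needed to say where this trial would fall.

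The band-pass is a secondary cost in precision for the PDD, and a small one for DSNBACK unless its blocks last about 60 s or longer. The documents do not support the stronger claims that the filter itself distorts group differences or that first-level degrees of freedom undermine the group tests. The stated sample size is not affected.

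**What to change.** - In C7a, delete the statement that task and rest are handled identically, and limit the band-pass and whole-brain regression to resting-state runs.
- For task runs, model drift (high-pass or polynomial terms), motion parameters and censoring inside the first-level model: 3dDeconvolve for the PDD, and the corresponding model for DSNBACK.
- State which list governs task runs, and reconcile 4 mm with 6 mm smoothing and Talairach with MNI-152.
- If either step is kept for task data, justify it, filter the regressors in the same model as the data, and report the ROI results with and without whole-brain regression.

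The cost is a change of wording and a re-run of task preprocessing from the stored raw images. No new data are needed.

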We will also consider alternative tasks to test differential attention to drug cues, particularly if the first sample of 12 subjects does not perform as expected. For example, a drug word Stroop (Marhe et al., 2013) with substitution of nicotine and alcohol stimuli could be an alternative. We are planning to pilot alternatives before the project starts so they will be available.

C4. Resting State Functional Connectivity Analysis: We will use the methods of the [name] Laboratory (Miranda-Dominguez et al., 2014) to analyze the rsMRI scans. We will use an ROI-to-ROI approach to calculate connectivity in the pre-processed data, based on the *a priori* regions previously associated with alcohol effects (**Table 3**). Bivariate correlations between the average (BOLD) signal from these regions provide connectivity estimates. Several sources of spurious variance along with their temporal derivatives are then removed from the data through linear regression (e.g., signal from ventricular regions and signal from the white matter). The magnitude of connectivity changes between AUD, NUD, NAUD and CS groups will be compared utilizing two-tailed t-tests. Finally, the raw p values will be corrected for multiple comparisons and thresholded at a false discovery rate (FDR) correction of $P_{FDR} < 0.05$.

ROI	CM x	CM y	CM z	
R/L ACC-SMA	±3	23	42	Sal
R/L MFG (DLPFC)	±38	18	44	Exec
R/L SFG (DMPFC)	±16	18	55	Exec
R/L PPC	±44	-60	36	Exec
R/L PCC	±3	-30	32	Def
R/L rINS	±32	19	1	Sal
R/L rMFG	±39	46	13	Exec
R/L IFG	±55	30	6	Sal
R/L AMYG	±28	-1	-19	Dal
R/L RS	±10	5	-9	Sal
BS	0	-22	-12	Sal

Table 3: Center of mass (CM) for *a priori* ROIs for planned comparison of multimodal imaging measures (SA1). ACC-SMA: anterior cingulate cortex-supplementary motor area, (r)MFG: (rostral) middle frontal gyrus, SFG: superior frontal gyrus, PPC: posterior parietal cortex including angular gyrus (AG), supramarginal gyrus (SMG) and inferior parietal lobule (IPL), PCC: posterior cingulate cortex. rINS: rostral insular cortex, RS: rostral striatum, IFG: inferior frontal gyrus, AMYG: amygdala, BS: brainstem. Sal: salience, Exec: executive.

C5. Cortical Density (VBM) and White Matter Integrity (DTI): These analyses are described in **C7**.

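### C7a lists band-pass filtering before motion regression and gives the motion parameters no matching filter, so part of the resting-state motion artefact would survive that step

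*Combined protocol and SAP*

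**What the plan says.** C7a states that "Task-related and resting-state fMRI data will be preprocessed identically". After segmentation it lists the steps in this order: "we apply a temporal bandpass filter (0.009 Hz < v < 0.08Hz), spatial smoothing" (6 mm kernel), then "regression with the 6 rigid body motion parameters, regression of the whole brain signal", then regression on ventricle and white-matter signals. It does not say whether the motion parameters are filtered, or whether filtering and regression are done jointly.

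C7a also limits scans to less than 3 mm of movement and plans despiking and motion censoring. It gives no censoring threshold and no place for censoring in the sequence. Its later list of AFNI commands has a 4 mm blur and no band-pass step, so the exact sequence is not fully fixed.

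C4 takes bivariate ROI-to-ROI correlations as the connectivity estimates. The next sentence reads: "Several sources of spurious variance along with their temporal derivatives are then removed from the data through linear regression". Its examples are ventricle and white-matter signals; motion is not named. The groups are then compared by t-tests with FDR correction. C6 uses the same correlation matrices as SVM features.

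**The concern.** Once the images are filtered, only motion artefact between 0.009 and 0.08 Hz remains in them. An unfiltered motion trace also carries power outside that band. The regression has to fit one coefficient to the whole trace, and the out-of-band part, which has no counterpart in the images, pulls the coefficient towards zero. Too little in-band artefact is subtracted, and the subtraction itself adds out-of-band motion to data that had been cleared of it.

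Residual motion that two ROIs have in common adds to their correlation without any neural cause. If the four groups differ in head motion, the residue could appear as a group difference in connectivity under C4 and as usable information for the classifier under C6. This point is confined to the resting-state data.

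**Working it through.** **Inputs from the documents**
- Pass band 0.009–0.08 Hz (C7a).
- TR 2 s: "TR/TE/α=2000 ms/38 ms/55" (C7).
- Task runs: "310 volumes per run", stated as 10.3 minutes (C7).
- Resting state: "Identical to fMRI settings with 200 volumes" (C7).

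**Check of the TR.** 310 × 2 s = 620 s = 10.33 min, which agrees with the stated 10.3 min. The resting run is 200 × 2 s = 400 s = 6.67 min. The documents give no figure for residual motion, so there is no other figure to reproduce.

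**Width of the band.** Nyquist frequency = 1/(2 × 2 s) = 0.25 Hz. Share of the frequency range kept = (0.08 − 0.009)/0.25 = 0.284.

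**One motion trace, by algebra.** Let m be the raw trace, Bm its filtered version, and f the share of its power inside the band. Regressing Bm on m gives a slope of f, not 1. The residual is Bm − f·m = (1 − f)·Bm − f·(m − Bm). Hence:
- in-band amplitude left: 1 − f
- in-band variance left: (1 − f)²
- out-of-band variance put back, relative to the original in-band artefact variance: f²(1 − f)/f = f(1 − f)

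For white motion f = 0.284. Amplitude left is 0.716, variance left is 0.716² = 0.513, and variance put back is 0.284 × 0.716 = 0.203. More than half the variance stays only if f < 1 − √0.5 = 0.293. More than half the amplitude stays if f < 0.5.

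**Six traces, by simulation.** Settings: 200 volumes, TR 2 s, artefact a random linear mix of six traces, 500 to 1,500 runs per setting. The spectra are assumptions. Entries are median percentages of the original in-band artefact variance; the put-back column is without detrending.

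| Assumed motion | Left in band | Left, traces detrended | Put back out of band |
|---|---|---|---|
| White | 50 | 49 | 20 |
| Spikes | 50 | 50 | 20 |
| 1/f^0.5 | 34 | 32 | 24 |
| 1/f | 26 | 21 | 22 |
| 1/f^1.5 | 29 | 19 | 18 |
| 1/f² | 36 | 21 | 15 |
| Random walk | 37 | 23 | 15 |
| Steps | 38 | 22 | 15 |

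For white motion the simulation agrees with the formula (50% against 51%). For undetrended random-walk motion (f about 0.20) the one-trace formula would give (1 − 0.203)² = 64%, against 37% with six traces, so the simulated values are used there. On the amplitude scale, 20–50% of variance is √0.20 = 0.45 to √0.50 = 0.71.

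**Sensitivity**
- Motion already concentrated in the band (f = 0.82) leaves only 3%.
- Adding derivatives of the motion parameters brings white motion down to 28%.
- Adding a whole-brain regressor assumed to carry the artefact along with other signal leaves 14–17%.
- Giving the regressors the same filter, or regressing first, leaves 0.000 in band and puts nothing back, for every spectrum tried. This is exact only for artefact linear in the six parameters.

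**The case against.** The strongest reply is that C7a is silent on the regressors; it does not say they are unfiltered. The listing may be loose, the AFNI list differs from it, and C4 relies on a cited laboratory's method that may settle the matter. It is true that unfiltered regressors are an inference. But the written order is explicit, nothing in the documents supplies the matching filter, and an analyst following the text would get the result above.

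The second reply is that other steps catch the residue, and much of this stands. Whole-brain regression is planned, and if that signal is taken from the filtered images it has no filter mismatch. In a simulated setting with artefact shared across regions, mean false correlation between unrelated ROIs was 0.11–0.14 after motion regression alone. It fell to about −0.02 once whole-brain regression was added, the same as with matched filtering. A reader might infer from the mechanism that a false correlation or group difference of a definite size follows. The documents do not support that: such a figure would have to ignore a planned step and assume a group difference in motion that is nowhere reported. The 3 mm limit, despiking and censoring reduce the residue further, although censoring targets spikes more than slow drift. None of these steps corrects the mismatch, and artefact that differs between regions is not fully removed.

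A reader might also take C4 to mean that nuisance signals are removed after the correlations are computed. Regression on the data cannot sensibly follow the correlation, and C4 starts from preprocessed data, so this is a matter of drafting.

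**Conclusion.** The point holds in a limited form. The order in C7a, with no matching filter stated for the motion parameters, is worse than an available alternative. About 20–50% of in-band motion variance survives the motion regression under the assumed spectra, less if motion lies mostly in band or derivatives are added, and some out-of-band motion is put back.

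It would be too strong to say that most of the artefact stays. That is true only on the amplitude scale and for some spectra; by variance it is at most about half in the settings tried.

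The effect on the final connectivity estimates cannot be sized from the documents. It depends on how far the artefact varies between regions after whole-brain regression, and on whether the groups differ in head motion. No false correlation or group difference of a given size is claimed. The change is still worth making before analysis, because the correction is exact for linear artefact and cheap.

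**What to change.** For the resting-state data, amend C7a in one of two ways:
- do the band-pass and all nuisance terms (motion parameters, whole-brain, ventricle and white-matter signals, censored frames) in one regression; or
- apply the same 0.009–0.08 Hz filter to every nuisance regressor before using it.

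State where censoring falls in the sequence. Reword C4 so that ROI correlations are computed after nuisance removal.

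The cost is a script change, a few sentences in C7a and C4, and some degrees of freedom per scan. The filter keeps 28 of 100 frequency bins, or about 2 × 28 = 56 degrees of freedom from 200 volumes. Six motion and three tissue regressors leave 56 − 9 = 47, before any derivatives or censored frames. No new data are needed.
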